Both study drug and placebo will be dispensed by the BWH Investigation Drug Service in 3-month allotments either in person at the screening visit, other non-study related office visit at BWH, or directly to the patient within 2 business days of the enrollment visit via mail or courier in accordance with BWH Investigation Drug Service policy. Subsequent allotments will be dispensed via mail or courier in accordance with BWH Investigation Drug Service policy. Our Research Nurse will communicate with study subjects by telephone at 3 months intervals in advance of releasing a 3-month allotment of study drug or placebo to ensure that treatment is not interrupted due to the subjects' supplies running out.

Randomization

Subjects who are 18 years of age or older with provoked DVT and/or PE, have completed at least 3 months of therapeutic anticoagulation, have a low risk of bleeding, and have at least one persistent provoking risk factor will be randomly assigned by computer in a 1:1 ratio to receive apixaban 2.5 mg orally twice daily or oral placebo for extended secondary prevention of VTE for a duration of 12 months.

Safety Outcomes

Primary Safety Outcome

The primary safety outcome will be major bleeding at 12 months. Major bleeding is defined as overt bleeding that is associated with a decrease in the hemoglobin level \geq 2 g/dL, leads to transfusion \geq 2 units of packed red blood cells, occurs in a critical site, or contributes to death (27). The primary safety outcome will be independently adjudicated by a blinded Clinical Endpoints Committee (CEC) review.

Secondary Safety Outcome

Clinically relevant non-major bleeding at 12 months will be evaluated (please see below) and is defined as overt bleeding that does not meet the criteria for major bleeding but that is associated with the need for medical intervention, unscheduled contact with a physician, interruption or discontinuation of the study drug, or discomfort or impairment of activities of daily living (28).

Efficacy Outcomes

Primary Efficacy Outcome

The primary efficacy outcome will be symptomatic, recurrent VTE, defined as the composite of deep vein thrombosis and/or pulmonary embolism at 12 months. The primary efficacy outcome will be independently adjudicated by a blinded CEC review.

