- **Non-hemorrhagic:** an ischemic focal neurological deficit (and not due to hemorrhage) that appears and is still partially evident at 24 hours.
- **Infarction with hemorrhagic conversion:** no evidence of hemorrhage on an initial scan, but found on a subsequent scan and is clinically relevant to the event, as determined by a neurologist.
- **Unknown type/no imaging performed:** the type of stroke could not be determined by imaging or other means (lumbar puncture, neurosurgery).

Cardiovascular death is defined as a death for which a definite non-cardiovascular cause (e.g. cancer) has not been identified. Uncertain causes of deaths are presumed to be cardiovascular unless proven otherwise.

Major adverse limb events include acute limb ischemia (ALI) and critical limb ischemia (CLI) (30). Acute limb ischemia is defined as limb-threatening ischemia which is confirmed by limb hemodynamics or imaging and leads to an acute vascular intervention (i.e. pharmacologic [heparin, thrombolysis], peripheral arterial surgery/reconstruction, peripheral angioplasty/stent, or amputation) within 30 days of onset of symptoms. In the absence of confirmation by limb hemodynamics or imaging, absent pedal pulses is acceptable as hemodynamic criterion for acute limb ischemia. If the event does not meet the definition for ALI it may be classified as

chronic limb ischemia, peripheral vascular intervention or other peripheral vascular hospitalization.

CLI is defined as continuing ischemic limb, foot or digit pain leading to hospitalization and intervention and not meeting the definition of ALI, or Fontaine 3 or 4 at baseline with peripheral intervention during the trial.

Peripheral vascular intervention is defined as peripheral vascular intervention not meeting the definition for ALI or CLI.

Additional Study Outcomes: Admission for heart failure will also be assessed at 12 months. Adherence to the twice-daily regimen of apixaban (and placebo) will be recorded as the total number of doses taken divided by the total number of doses prescribed. Adherence data will be recorded on patient-maintained drug diaries.

Clinical Endpoints Committee Adjudication of Study Outcomes

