Routine laboratory testing is neither recommended nor required in patients receiving extended duration apixaban, including the 2.5 mg twice daily dosing regimen. Patients enrolled in the study will either have been identified from one of the practices of our Vascular Medicine faculty or will be assigned to one of our faculty for long-term management of VTE. Accordingly, every patient enrolled in the study will have ongoing medical care with a dedicated Vascular Medicine provider. Study patients will be encouraged to follow-up with their primary care, , and other appropriate clinicians. Specifically, at the end of the treatment visit, every patient will be reminded to follow-up with a PCP as dictated by routine care and best clinical practice. Demographic, clinical characteristics, medication records, and outcomes will be abstracted from the BWH Electronic Health Record (EPIC).

When our Research Nurse conducts the every 3-month telephone call in advance of releasing a 3-month allotment of study drug or placebo the subject will be queried for any issues with the study or adverse events.

We will conduct an end-of-treatment visit to obtain data relevant to the study end points.

We will assess medication adherence via pill count. Medication adherence will be calculated in three month intervals as the total number of doses taken divided by the total number of doses prescribed for that time period ($[x / 180] \times 100$ = medication adherence [%]) and also for the total 360-day study period ($[x / 720] \times 100$ = medication adherence [%]). Subjects will be given a study drug diary to fill out at home each day. Subjects will write down the time they take their study drug and any side effects. The study drug diary will be collected at a regularly scheduled office visit or the end-of-treatment visit at conclusion of the study period.

Subject Retention, Withdrawal, and Termination

Continued participation of study subjects will be encouraged at the time of outpatient evaluation through the 12-month follow-up interval. However, study subjects will be informed that they retain the right to withdraw from the study at any time without compromise to their current or subsequent medical care. Subjects will be terminated from the study if they expire or elect to withdraw.

If study subjects elect to withdraw, they will be asked for permission to do the following:

1. Be contacted by telephone **AND**
2. Have their physicians contacted

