Date study drug stopped	 /  /  MM DD YYYY Completed full 12 months of study drug?  Yes  No If did not stay on drug for 12 months, reason why not?  Fulfilled criteria for a primary study outcome (recurrent VTE or major/clinically relevant non-major bleed)  Patient expired  Adverse drug event or side-effect  Change in clinical status (such as change in goals of care, comfort measures, hospice care)  Patient preference/withdrawal of consent
Medication adherence (via pill count)	Total doses taken/total doses prescribed = ( / 720) x 100 =  %

12-Month Study Outcomes	
Deep vein thrombosis	 Yes  No If yes, date  /  /  MM DD YYYY Confirmed by diagnostic imaging:  Yes  No If yes, by?  Ultrasound  CT  MRI  Venography

	
Location:
 
 Upper extremity
 
If checked:
 
 Bilateral or SVC
 
 Lower extremity
 
If checked:
 
 Bilateral or IVC
 
 Proximal (popliteal or higher)
 
 Calf
 
Hospitalized?
 
 Yes
 
 No
 
Treatment:
 
 Anticoagulation
 
 Pharmacomechanical (catheter-based) therapy
 
 Surgery
 
 IVC filter

Superficial vein thrombosis	
 Yes
 
 No
 
If yes, date _____ / _____ / _____ MM DD YYYY

Other venous thrombosis (mesenteric, cerebral sinus, gonadal, etc.)	
 Yes
 
 No
 
If yes, date _____ / _____ / _____ MM DD YYYY

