4.2.2 Secondary Safety Outcome

The time to first clinically relevant non-major bleeding within 12 months will be evaluated and is defined per the ISTH as overt bleeding that does not meet the criteria for major bleeding but that is associated with the need for medical intervention, unscheduled contact with a physician, interruption or discontinuation of the study drug, or discomfort or impairment of activities of daily living 2. Like the primary safety outcome, this outcome will be assessed by the CEC, blinded to assigned treatments. All-cause death will be considered a competing risk for this outcome. We will also assess a composite outcome of major bleeding and clinically-relevant nonmajor bleeding. Non-hemorrhagic death will be considered a competing risk for these outcomes.

For all the outcomes, the last time contact date will be used for determining censoring.

5. Details of Randomization and Blinding

Subjects who are 18 years of age or older with provoked DVT and/or PE, have completed at least 3 months of therapeutic anticoagulation, have a low risk of bleeding, and have at least one enduring risk factor will be randomly assigned by computer in a 1:1 ratio to receive apixaban 2.5 mg orally twice daily or oral placebo for extended secondary prevention of VTE for a duration of 12 months.

This study will be conducted in a blinded fashion. To maintain blinding of study treatment, the active study drug and placebo will be matched for color, size and box. Subjects, investigators, members of any of the administrative and adjudicating committees, and the Sponsor's staff conducting the study, will not have access to individual subject treatment assignments.

An independent Safety Monitor has been selected for this study. The Safety Monitor is an expert in VTE and is distinct from the DMSB and Study Staff and will be available throughout the study to assess patient safety issues that may arise, objectively. The Safety Monitor will have the ability to break the blind of a study patient as the need arises (immediately, in real-time). If the Safety Monitor is unavailable because of travel, one of the Physician Study Investigators will serve as back-up.

6. Statistical Plan

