6.2 Cohort Definition

In this section, we define a main cohort and four confirmatory cohorts for the analysis of efficacy and safety (**Table**).

Main Cohort (ITT): we will use the intention-to-treat (ITT) cohort since it maintains the original randomization scheme ("as randomized")⁵.

Confirmatory Cohort (MITT): the modified intention-to-treat (MITT) cohort consisting of all randomized patients who took at least one dose of the assigned treatment and did not undergo post-randomization exclusion.

Confirmatory Cohort (PP-1): Additional analyses will include a per-protocol (PP) population for subjects who took 80% of the study drug (or placebo).

Confirmatory Cohort (PP-2): Additional analyses will include a per-protocol (PP) population for subjects who took 80% of the study drug (or placebo) with censoring for either ISTH major bleeding or clinically relevant nonmajor bleeding event.

Confirmatory Cohort (Safety Cohort): In this cohort, we will only consider bleeding events (major bleed or clinically relevant non-major bleed) that occurred within 96 hours of taking a dose of the study drug (or placebo). The follow-up duration will be considered until the occurrence of a bleeding event or 96 hours after taking the last dose of the study drug (or placebo), whichever comes first.

6.2.1 Table. Analysis cohorts.

Analysis Set	Definition	Primary Efficacy-12-month recurrent symptomatic VTE	Primary Safety-12-month ISTH major bleeding
ITT	All randomized	Number of events Proportion Cumulative incidence Hazard ratio 95% confidence interval P-value	Number of events Proportion Cumulative incidence Hazard ratio 95% confidence interval
mITT	All randomized who took at least one dose of assigned treatment (apixaban or placebo) and did not undergo post-randomization exclusion	Number of events Proportion Cumulative incidence Hazard ratio 95% confidence interval	Number of events Proportion Cumulative incidence Hazard ratio 95% confidence interval
Per protocol without censoring for bleeding events	Subjects who took 80% of assigned treatment doses (apixaban or placebo)	Number of events Proportion Cumulative incidence Hazard ratio 95% confidence interval	Number of events Proportion Cumulative incidence Hazard ratio 95% confidence interval

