Per protocol with censoring for bleeding events	Subjects who took 80% of assigned treatment doses (apixaban or placebo) with censoring for either ISTH major bleeding or clinically relevant nonmajor bleeding event	Number of events Proportion Cumulative incidence Hazard ratio 95% confidence interval	Number of events Proportion Cumulative incidence Hazard ratio 95% confidence interval
Safety set	Subjects who took at least one dose of the study drug (or placebo) until	Number of events Proportion Cumulative incidence Hazard ratio	Number of events Proportion Cumulative incidence Hazard ratio

	96 hours after the administration of the last dose of the study drug.	95% confidence interval	95% confidence interval P-value
--	---	-------------------------	---

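### The per-protocol 80% rule is not tied to an adherence measure; on the protocol's only whole-study measure, about 80% of VTE patients cannot enter PP-1 or PP-2, and PP-2 censors at the major bleeds that it is meant to count

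*Combined protocol and SAP*

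**What the plan says.** SAP section 6.2 names a main ITT cohort and four cohorts that it calls confirmatory. Two of these are per protocol. Table 6.2.1 defines PP-1 as "Subjects who took 80% of assigned treatment doses (apixaban or placebo"). PP-2 uses the same threshold "with censoring for either ISTH major bleeding or clinically relevant nonmajor bleeding event". Both rows ask for event counts, proportions, cumulative incidence, a hazard ratio and a confidence interval for recurrent VTE and for ISTH major bleeding. Neither row asks for a p-value.

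The SAP gives no adherence formula and does not refer to one. The protocol does have one. Under Additional Study Outcomes, adherence "will be recorded as the total number of doses taken divided by the total number of doses prescribed". Under Follow-Up Evaluation it is worked out as x/180 for each three-month interval "and also for the total 360-day study period", where it is x/720. The Case Report Form has a single adherence field, "Total doses taken/total doses prescribed", with 720 printed as the denominator.

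The protocol section on managing recurrent VTE requires study drug to stop at a confirmed recurrence and keeps the patient in follow-up. Major bleeding is listed among the withdrawal criteria. On censoring, SAP section 4.2.2 says: "For all the outcomes, the last time contact date will be used for determining censoring".

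**The concern.** A recurrent VTE ends dosing, so a fixed 12-month denominator makes membership of the per-protocol set depend on the primary outcome. A patient leaves the set because treatment failed, not because of poor adherence. The same mechanism reaches major bleeding wherever a bleed ends dosing early.

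The SAP calls these sets confirmatory and reports both primary outcomes in them. If most VTEs are removed by construction, the sets show misleadingly low event rates and too few events to corroborate or challenge ITT. A programmer who has to choose the denominator after the fact may also be choosing with the data in view.

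The second problem needs no assumption about timing. PP-2 censors at major bleeding and is then asked to count major bleeding.

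**Working it through.** **The plan's own figures.** Two doses a day gives 360 × 2 = 720 and 90 × 2 = 180, as the protocol states. The design of 6% versus 1.5% with 279 per group gives power 0.8005 (Pearson chi-squared, two-sided 0.05), which matches the protocol's Stata output.

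**Inputs.** From the protocol: 300 per arm, 12-month VTE risk 6% on placebo and 1.5% on apixaban. Assumed, because the documents do not give them: when events occur within the year, and adherence before the event. The base case is constant hazard and perfect adherence until the event.

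**Cut-off.** 0.80 × 720 = 576 doses; 576 / 2 = day 288. A patient whose drug stops for a VTE before then cannot qualify.

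**Share of VTEs excluded.** With H = −ln(1 − p) and F(t) = 1 − exp(−H(t/360)^k), the share is F(288)/p.
- Constant hazard (k = 1): 80.5% for p = 0.06 and 80.1% for p = 0.015.
- Early events (k = 0.7, p = 0.06): 85.9%.
- Late events (k = 1.5, p = 0.06): 72.2%.
- 90% adherence before the event (k = 1, p = 0.06): the cut-off becomes 288/0.9 = day 320, and 89.2% are excluded.

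**What remains at constant hazard.**
- ITT expectation: 300 × 0.06 + 300 × 0.015 = 18 + 4.5 = 22.5 events.
- Left in the PP set: 3.51 + 0.89 = about 4.4 events.
- In-set incidence: 3.51/285.5 = 1.2% and 0.89/296.4 = 0.3%, instead of 6% and 1.5%.
- Risk ratio in the set: 0.245. The planned hazard ratio is ln(0.985)/ln(0.94) = 0.244. The point estimate hardly moves, because both arms lose about the same share of events.

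**Precision.** The approximate SE of the log hazard ratio is √(1/d₀ + 1/d₁), where d₀ and d₁ are the events per arm.
- ITT: √(1/18 + 1/4.5) = 0.527, interval 0.09 to 0.69.
- PP at constant hazard: √(1/3.51 + 1/0.89) = 1.18, interval 0.02 to 2.5.
- PP with late events, the most favourable timing tried: 5.01 + 1.27 events remain, SE 0.99, interval about 0.03 to 1.7.

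On the 720 measure the expected interval therefore includes 1 even in the most favourable of these cases, although the planned effect is true.

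**PP-2.** Set the PP-2 row against its safety cell. Censoring is at the first major or clinically relevant non-major bleed. The cell asks for the number of major bleeds, their cumulative incidence and a hazard ratio. Read literally, every major bleed is censored and the cell is empty. If a major bleed is counted on the day that it censors, any major bleed that follows a non-major bleed is still lost. No tie rule is given.

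**The case against.** The best defence is that the documents do contain a denominator. The protocol and the Case Report Form both give 720, so a reader who infers that no denominator exists anywhere would be wrong. That stands, but it does not rescue the rule: 720 is the measure that removes about 80% of VTEs.

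A reader might also treat several denominators as equally open. One candidate is doses in the allotments released so far, because the nurse calls "at 3 months intervals in advance of releasing a 3-month allotment of study drug or placebo"; that would exclude about 50% of VTEs. The documents never use released allotments as an adherence denominator, so the 50% figure is inference and the point does not rest on it. Nor would the interval reliably include 1 on that reading: with late events (k = 1.5), 10.8 + 2.7 events remain and the upper limit is about 0.92. Applying the protocol's interval measure, x/180, to the interval in which the event falls also excludes about 80%.

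Other analyses avoid the 80% rule. The mITT set has none, and the safety-set row of Table 6.2.1 has a VTE column running to 96 hours after the last dose. PP-1 and the safety set also report major bleeding, so the PP-2 contradiction need not lose a result altogether. These points limit the damage and hold the severity down. They do not make the PP rows usable as written.

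**Conclusion.** The concern holds for the per-protocol sets. If the SAP's 80% threshold is applied to the only whole-study measure in the documents, about 80% of VTEs are excluded by construction. The range is 72% to 86% over Weibull shapes 1.5 to 0.7, and about 89% with 90% prior adherence. These shares rest on assumed event timing and prior adherence, and on the planned 6% versus 1.5%; none of them is a figure from the documents. The day-288 cut-off and the PP-2 contradiction do not depend on those assumptions.

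A reader might infer that the primary result or the estimated treatment effect is distorted. The documents do not support that. The main analysis is ITT, and Table 6.2.1 asks for a p-value only for VTE in ITT and for major bleeding in the safety set. The PP hazard ratio stays near 0.25. What is lost is the absolute VTE rates in PP-1 and PP-2 and their ability to corroborate or question ITT. Severity is minor to moderate.

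**What to change.** 1. Define PP adherence as at least 80% of doses due from the first dose to the earliest of first adjudicated VTE, major bleed, death, permanent discontinuation of study drug, or month 12. No VTE is then excluded merely because it stopped dosing.

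2. Add a follow-up rule for the PP sets. With the new denominator and censoring at last contact, a fully adherent patient who stops permanently on day 10 would enter PP-1 and could bring 360 − 10 = 350 off-drug days. Censor a fixed time after the last dose. The SAP's safety cohort already ends follow-up at a bleed or "96 hours after taking the last dose of the study drug (or placebo), whichever comes first", and that window could be reused. Count a VTE or major bleed that causes the stop on its own date.

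3. Apply the PP-2 bleeding censoring to the VTE column only and drop the PP-2 major-bleeding cell. PP-1 and the safety set already cover that outcome.

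4. State the downside. Censoring at discontinuation may be informative, and early stoppers contribute only short follow-up. The PP results should therefore be described as supportive of ITT.

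The cost is a few lines of SAP text and minor programming. Pill counts, dose diaries and drug start and stop dates are already collected. Nothing in trial conduct or patient management changes.

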6.3 Baseline Demographics and Clinical Comorbidities Description

Understanding the baseline demographics and clinical comorbidities of a cohort is crucial for interpreting study results and drawing conclusions about the generalizability of findings. In the HI-PRO trial, a table of descriptive statistics will be provided to summarize the baseline demographics of the intention-to-treat cohort. The table will include information on logical and categorical variables, such as age, sex, race, and comorbidities. The numbers and percentages will be provided for these variables, allowing for an assessment of the distribution and prevalence of different characteristics among the study population. In addition to logical and categorical variables, the table will also provide information on continuous variables, such as body mass index, hemoglobin level, and serum creatinine level. For these variables, the mean and standard deviation (SD) will be provided to summarize the central tendency and variability of the data.

According to the recent statistical reporting guideline from some experts⁶, we will not provide p-values for testing the differences in baseline characteristics of the two assigned groups. However, the balances should be checked to see the quality of randomization by inspecting the standardized difference. We will consider the ones with a standardized difference >0.1 as clinically different. For a certain category whose observations are smaller than five counts, we may consider regrouping the categories.

6.4 Survival Analysis

6.4.1 Principal Analysis

We first provide analysis without adjustment of baseline demographics. For both the primary and secondary efficacy outcomes and principal and secondary safety outcomes, we use the Kaplan-Meier curve to estimate the survival functions of each group. If there is a presence of competing risks, cumulative incidence functions (CIFs) will be used to estimate the survival function⁷. The two-side log-rank test is used to measure if the apixaban 2.5 mg twice a day has a better survival chance than placebo (i.e., better chance of meeting the primary outcome). If there is a presence of competing risk, the log-rank based on cause-specific hazards⁸ will be used. The corresponding hazard ratio of treatment effect and its confidence interval will be reported.

While our analysis is based on randomization, we also provide confirmatory analyses with the adjustment of baseline demographics and clinical comorbidities since it may capture any potential variations to make the statistical analysis more powerful. We use Cox regression to assess both the primary and secondary efficacy outcomes, while with adjustment of baseline demographics and clinical comorbidities. No interaction effects will be added. If there are competing risks, a cause-specific hazard model⁷ will be used. The hazard ratio for being treatment with the apixaban 2.5 mg twice a day will be used to test the treatment effect. The hazard ratio of other baseline demographics will be reported as supplementary information.

If the trial has a good randomization, we expect that the hazard ratio of treatment in analysis with the adjustment of baseline demographics and its p-value implies the same conclusion as in analysis without adjustment of baseline demographics. However, if they are not consistent in

clinical interpretation, i.e., a) the interpretation directions are different; b) p-values indicate different conclusion of significance, we will use the hazard ratio of treatment in analysis with the adjustment of baseline demographics as the main results to report, and the results of unadjusted one is treated as supplementary materials.

